3.5.5 Day 7 (+2 Days); Follow-up Visit

Patients will visit the clinic on Day 7 to have gynecological examination performed. The Investigator or an authorized designee will assess the presence of vulvovaginal signs (erythema, edema, or excoriation) and symptoms (itching, burning, or irritation) and score each sign and symptom.

Vaginal samples will be examined by microscope to reveal yeast forms (hyphae or pseudohyphae) or budding yeast and secretion samples collected by swab to be used for sequencing analysis of the vaginal microbiome. Vaginal pH will also be assessed.

If VVC symptoms are still present, patients will have prolonged treatment and receive additional doses of investigational product to be administered at home on Day(s) 7, 9, 11, and 13.

In addition, patients will be asked questions from the patient questionnaire to assess: usability; concomitant medications; and AEs, if any.

Procedures performed:

- Gynecological examination by Investigator or authorized designee evaluating signs (erythema, edema, or excoriation) and symptoms (itching, burning, or irritation of VVC according to the scoring scale
- Fungal KOH microscope assessment
- Vaginal swab for sequencing
- Vaginal pH
- Recording of:
 - concomitant medications,
 - adverse events, and
 - usability
- Treatment dispensing and self-administration by patients if receiving prolonged treatment

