## 4 Study design

This is an open-label, single-armed, multi-center study to evaluate clinical performance, tolerability, and safety of Gedea Pessary in 24 adult women with VVC. Patients seeking treatment can be screened for study participation. Included patients will have gynecological examination, including collection of CVVS data, vaginal samples taken, and will receive the investigational product to be self-administered at Day(s) 0, 2, 4, and 6. Patients will again be examined after 7 days and CVVS data will be collected. Prolonged treatment at Day(s) 7, 9, 11, and 13 will be given to patients not cured at Day 7; including re-examination at Day 14. Patients will be followed up by telephone up to 29 days after last treatment administration. Vaginal samples will be used for confirming diagnosis and microbiome analyzes. Patient questionnaires will be used for assessing VVC symptoms, usability, and AEs.

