## Figure 1 Study Flow Chart

VVS = Vulvovaginal Symptoms, VS = Vaginal Swab, CVVS = Composite Vulvovaginal Signs and Symptoms

**Patients not receiving prolonged treatment** applies to patients cured at Day 7. If not cured, the flow chart **patients receiving prolonged treatment** applies. Patients will here receive fluconazole if not cured at Day 14. Adverse events will be assessed throughout the study

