### 6.1 *Clinical Performance Assessments*

Assessments described below in [Section 6.1.1](#), gynecological examination, will be used to collect the following 6 vulvovaginal signs and symptoms:

- Vulvovaginal signs of: erythema, edema, and excoriation; and
- Vulvovaginal symptoms of itching, burning, and irritation.

The intensity of each of the signs and symptoms will be scored as:

- 0 = none (absent),
- 1 = mild (slight),
- 2 = moderate (definitely present), or
- 3 = severe (marked, intense).

The scores will be added together and the sum defined as the CVVS score.

A CVVS score equal to or below 3 on Day 7 will be defined as clinical cure, and is a co-primary study endpoint together with safety and tolerability evaluation.

The CVVS score will also be used for the following secondary endpoints:

- Proportion of patients having a reduction in CVVS score on Day 7 compared to Day 0.
- Change in the CVVS score from Day 0 to Day 7.
- Recurrence rate at Day 14 and Day 35, defined as the proportion of patients clinically cured at Day 7 and thereafter responding "yes" to a yes/no question from the patient questionnaire on whether the symptoms have recurred.
- Proportion of patients receiving prolonged treatment.
- Clinical cure rate on Day 14, defined as the absence of signs and symptoms of VVC in terms of having a CVVS score equal to or below 3.
- Proportion of patients having a reduction in CVVS score on Day 14 compared to Day 0.

- Change in the CVVS score from Day 0 to Day 14.
- Recurrence rate at Day 21, and Day 42, defined as the proportion of patients clinically cured at Day 14 and thereafter responding “yes” to a yes/no question from the patient questionnaire on whether the symptoms have recurred.
- Proportion of patients receiving prescription for fluconazole at Day 14.

Assessments described in [Section 6.1.2](#), patient questionnaire, will be used to assess the following secondary endpoints:

- Proportion of patients having a reduction in the sum of the 3 vulvovaginal symptoms scores (itching, burning, and irritation) on Day 4 and Day 7, compared to Day 0.
- Change in the sum of the 3 vulvovaginal symptoms scores (itching, burning, and irritation) from Day 0 to Day 4 and Day 7.
- Usability, measured by patient questionnaire.
- Proportion of patients having a reduction in the sum of the 3 vulvovaginal symptoms scores (itching, burning, and irritation) on Day 11, Day 14, Day 21, and Day 42, compared to Day 0.

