### **7.1.1 Presentation of results**

If applicable, results will be presented together with the unit.

Continuous data will be summarised using descriptive statistics, and the following parameters will be reported:

- number of patients with evaluable observations and missing observations
- arithmetic mean and standard deviation
- median
- first and third quartiles
- minimum and maximum.

Categorical data will be presented using absolute frequency and percentage. When the absolute frequency is zero, the percentage will not be presented. Unless stated otherwise, the denominator for percentage calculations will be the total number of patients in the applicable analysis set, including patients with missing data. For variables with missing values, the number and percentage of patients with missing values will be presented.

Statistical testing will be performed using an overall significance level of 5%. The primary endpoint analysis will be based on one-sided testing, whereas the secondary endpoints analyses will be based on two-sided testing. Corresponding confidence intervals will be presented. See [Section 7.9](#) below for further information.

Data will be presented using an appropriate number of decimal places, to ensure that undue precision is not implied (e.g. the number of decimals should not exceed the accuracy of the measuring instrument). Raw data will be presented with the same number of decimals as collected, and derived data with an appropriate number of decimals based on general practice, mathematical rationale or scientific rationale.

Minimum and maximum values will be presented with the same number of decimals as the analysed variable and the other descriptive statistics will be presented with one decimal more. Percentages and proportions will be presented with one decimal. Confidence interval bounds will be presented with the same number of decimals as the corresponding point estimate, and p-values will be presented with 4 decimals or as '<.0001'.

Mock tables and graphs are presented in the Data Display Plan (DDP), which is a supplementary document to this analysis plan. Individual patient data listings will be presented according to the ICH E3 guideline for Structure and Content of Clinical Study Reports (2), unless stated otherwise.

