### 7.2.1 *Full analysis set*

Full Analysis Set (FAS): This is the primary population and comprises all patients entering the study and having received at least 1 dose of study treatment. Analyses of clinical performance will be performed against this population.

In addition to this, two sub-populations based on this FAS will be formed: “FAS (For patients not receiving prolonged treatment)”, and “FAS (For patients receiving prolonged treatment)”.

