#### C. For patients receiving prolonged treatment

- viii] Clinical cure rate on Day 14, defined as the absence of signs and symptoms of VVC in terms of having a CVVS score equal to or below 3

- ix] Proportion of patients having a reduction in CVVS score on Day 14 compared to Day 0
- x] Change in the CVVS score from Day 0 to Day 14
- xi] Proportion of patients having a reduction in the sum of the 3 vulvovaginal symptoms scores (itching, burning, and irritation) on Day 11, Day 14, Day 21, and Day 42, compared to Day 0
- xii] Change in the sum of the 3 vulvovaginal symptoms scores (itching, burning, and irritation) from Day 0 to Day 11, Day 14, Day 21, and Day 42
- xiii] Recurrence rate on Day 21, and Day 42, defined as the proportion of patients clinically cured on Day 14 and thereafter responding “yes” to a yes/no question from the patient questionnaire on whether the symptoms have recurred
- xiv] Proportion of patients receiving prescription for fluconazole on Day 14

The endpoints viii], ix], xi], xiii], and xiv] are binary variables.

The endpoints x] and xii] are considered as continuous variables.

In connection to the endpoints described above, the underlying variables listed below not constituting endpoints (denoted as “other related variables” in the CIP), will be presented descriptively.

- CVVS score (can take integer values in the interval 0-18)
- Vulvovaginal signs: erythema (can take integer values in the interval 0-3)
- Vulvovaginal signs: edema (can take integer values in the interval 0-3)
- Vulvovaginal signs: excoriation (can take integer values in the interval 0-3)
- Sum of all vulvovaginal signs score (can take integer values in the interval 0-9)
- Vulvovaginal symptoms: itching (can take integer values in the interval 0-3)
- Vulvovaginal symptoms: burning (can take integer values in the interval 0-3)
- Vulvovaginal symptoms: irritation (can take integer values in the interval 0-3)
- Sum of all vulvovaginal symptoms score (can take integer values in the interval 0-9)

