### ***8.8 Recurrence rate***

Recurrence rate is based on a binary variable, where a recurred patient is defined as a patient clinically cured on Day 7 and thereafter responding “yes” at specified follow-up visits to a yes/no question from the patient questionnaire on whether the symptoms have recurred.

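### The SAP's only derivation of recurrence uses cure on Day 7, while the Day 21 and Day 42 rates are defined everywhere else by cure on Day 14

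*SAP*

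**What the plan says.** SAP 8.8 is the only place where the recurrence variable is derived. It says "where a recurred patient is defined as a patient clinically cured on Day 7 and thereafter responding" yes at the specified follow-up visits. It has no separate rule for patients who receive prolonged treatment.

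The endpoint definitions distinguish two groups. For patients without prolonged treatment, the Day 14 and Day 35 rates are conditional on cure on Day 7, which agrees with 8.8. For patients with prolonged treatment, SAP 7.9.2 endpoint xiii has "Recurrence rate on Day 21, and Day 42, defined as the proportion of patients clinically cured on Day 14", and SAP 3.2.1 has the same. SAP 6.1 has "Recurrence rate at Day 21, and Day 42, defined as the proportion of patients clinically cured at Day 14". The Protocol synopsis, 2.2 and 6.1 agree with these.

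On who enters the prolonged-treatment group, SAP 4 says "Prolonged treatment at Day(s) 7, 9, 11, and 13 will be given to patients not cured at Day 7". The note to Figure 1 says that the chart without prolonged treatment "applies to patients cured at Day 7. If not cured, the flow chart" for prolonged treatment is used. Protocol 3.5.5 words it differently: "If VVC symptoms are still present, patients will have prolonged treatment".

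On denominators, SAP 7.2.1 says that "two sub-populations based on this FAS will be formed", one with and one without prolonged treatment. SAP 7.1.1 sets the default: "Unless stated otherwise, the denominator for percentage calculations will be the total number of patients in the applicable analysis set, including patients with missing data".

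**The concern.** Section 8 is where a programmer looks for the rule that turns raw data into an analysis variable. Here that rule conflicts with the endpoint it is meant to produce. The Day 21 and Day 42 rates are meant to show how often symptoms return in patients who needed a second course and were cured after it. Conditioning on cure on Day 7 asks about a different set of patients, and under one of the plan's two descriptions of that group the set is empty.

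The risk is a recurrence figure for prolonged treatment that looks favourable, or is missing, because of the definition and not the data. SAP 7.2.2 describes the recurrence analyses as important and creates a second per-protocol set for them, so the same variable would feed that set too. SAP 7.11 lists departures from the CIP in some detail, down to moving one endpoint under another heading. It lists nothing on recurrence, so 8.8 reads as a drafting slip and not as a decision.

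**Working it through.** **Step 1. The definitions side by side.**

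| Rate | Group | Cure visit in the endpoint definitions (SAP and Protocol) | Cure visit in SAP 8.8 |
|---|---|---|---|
| Day 14, Day 35 | No prolonged treatment | Day 7 | Day 7 |
| Day 21, Day 42 | Prolonged treatment | Day 14 | Day 7 |

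The first row agrees and the second does not. The Day 14 condition appears in six places: SAP 3.2.1, 6.1 and 7.9.2 xiii, and Protocol synopsis, 2.2 and 6.1.

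**Step 2. Literal 8.8 when entry follows SAP 4 and Figure 1.** Every patient in the prolonged group is, by definition, not cured on Day 7. None can meet the first condition of 8.8, so the numerator of endpoint xiii is 0 whatever the patients answer. The reported result then depends on the denominator:

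- Whole prolonged-treatment FAS sub-population (the 7.1.1 default applied to 7.2.1): 0/n.
- Patients cured on Day 7 within that group: 0/0, not estimable.

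**Step 3. Size of the group and of the empty result.** Inputs from SAP 5.1: N = 24 and an assumed true cure rate of 70%.

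- Expected n = 24 × (1 − 0.70) = 7.2, about 7 patients.
- The 5th and 95th percentiles of Binomial(24, 0.30) are 4 and 11.
- For a zero count, the upper limit of the two-sided 95% Clopper-Pearson interval (the method in SAP 7.9.2) is 1 − 0.025^(1/n).

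| n | Reported result | Exact 95% CI |
|---|---|---|
| 4 | 0/4 | 0 to 60.2% |
| 7 | 0/7 | 0 to 41.0% |
| 11 | 0/11 | 0 to 28.5% |

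These intervals would carry no information on recurrence, because the zero is fixed in advance.

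**Step 4. Literal 8.8 when entry follows Protocol 3.5.5 and 3.5.10.** There, prolonged treatment is tied to symptoms that persist on Day 7. Clinical cure is a CVVS score of 3 or less, so a patient with a total of 1 to 3 and a residual symptom can be cured and still enter the group. SAP 8.9 also identifies the group by doses received and not by cure status. The numerator under 8.8 is then not forced to zero. The selection is still wrong: a patient with a score above 3 on Day 7 who is first cured on Day 14 is left out, although the endpoint is about such patients. A patient cured on Day 7 but not on Day 14 could be counted, although the endpoint excludes her.

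**Step 5. What the Day 14 condition would give.** The numerator is the number of patients cured on Day 14 who then answer yes, and the documents give no Day 14 cure rate from which to predict it. The only figure needed is the cost in precision. For illustration, assume one recurrence and 5 of 7 patients cured on Day 14: 1/5 = 20.0% (0.5 to 71.6%), against 1/7 = 14.3% (0.4 to 57.9%) with the whole sub-population as denominator.

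**The case against.** The strongest reply is that the right definition is already in the SAP three times, including the analysis section itself. SAP 8.8 refers to specified follow-up visits without naming them, so it has to be read with 7.9.2. A sensible programmer would do that, and an endpoint with no possible events would be noticed at the first run. Table layouts are in a Data Display Plan that is not part of these documents and may settle the matter.

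Much of this stands. A reader might infer that endpoint xiii will be reported as zero or as not estimable. The documents do not support that: it happens only if 8.8 overrides the endpoint definition, and only if entry to prolonged treatment follows SAP 4 and Figure 1. Step 4 shows that under the Protocol 3.5.5 wording neither zero nor 0/0 is guaranteed.

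What does not stand is that the conflict is harmless. The SAP gives no order of precedence between Sections 7 and 8, and 8.8 is the text written to define the variable. Two competent programmers could follow different sections and report different results, each with a passage to cite.

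It is also tempting to estimate how many real recurrences would be hidden, using the 13% to 26% relapse range under Protocol Table 1. That range concerns other products in severe VVC, and the number cured on Day 14 would have to be invented. The point does not need it.

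**Conclusion.** The inconsistency is real and should be corrected. SAP 8.8 conditions every recurrence rate on cure on Day 7, whereas the Day 21 and Day 42 rates are defined by cure on Day 14, and no change is declared. Followed literally, 8.8 could select the wrong patients for endpoint xiii. With entry as in SAP 4 and Figure 1, the rate is fixed at zero with the default denominator, or undefined among patients cured on Day 7. With entry as in Protocol 3.5.5 and 3.5.10, the rate can be non-zero but omits patients first cured on Day 14.

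The group size of about 7 (4 to 11) rests on the plan's 70% cure rate, on 24 treated patients and on entry by Day 7 cure status. The conflict itself rests on no numerical assumption.

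The reach is limited. SAP 7.9.2 gives this endpoint an exact interval and no hypothesis test. The Day 14 and Day 35 rates have the correct cure condition in 8.8. A reader might suspect that the main result is affected, but the Day 7 cure rate does not use this variable.

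**What to change.** Rewrite SAP 8.8 with two branches:

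- **Day 14 and Day 35 rates (no prolonged treatment):** a recurred patient is one who was clinically cured on Day 7 and answers yes at the visit in question.
- **Day 21 and Day 42 rates (prolonged treatment):** a recurred patient is one who was clinically cured on Day 14 and answers yes at the visit in question.

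State in 8.8 that each rate is a proportion of the patients cured at the relevant anchor visit (Day 7 or Day 14), as an exception to the 7.1.1 default. How to treat a cured patient who did not answer the question is a separate choice that affects all four rates. It should be made on its own merits, with SAP 7.1.5 in view.

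The cost is SAP wording only. The Day 14 score and the Day 21 and Day 42 questions are already scheduled. The interval widens because the denominator shrinks; the 1/5 against 1/7 comparison in the working shows by how much in one assumed case.

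Separately, the passages on who enters prolonged treatment (SAP 4 and the Figure 1 note against Protocol 3.5.5 and 3.5.10) must be reconciled. That is a different defect, and correcting 8.8 does not resolve it.

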3.2.1 Risks and Benefits

The investigational device, Gedea Pessary has been evaluated in accordance with ISO 10993 (Biological Evaluation of Medical Devices). The evaluation included: cytotoxicity testing (Direct cell contact test, ISO 10993-5); *in vivo* irritation (Vaginal acute irritation; ISO 10993-10); and sensitization (local lymph node assay, ISO 10993-10). The *in vitro* cytotoxicity test, classified the test item as slight to moderate cytotoxic (scale 1–2 on a 3-grade scale); the *in vivo* irritation test as well as the *in vivo* sensitization test showed no signs of irritation, necrosis or sensitization after treatment with Gedea Pessary.

The vaginal pessary may, in similarity with other vaginally administered products, cause temporary minor discomfort at insertion. The vaginal sampling procedures are similar to sampling procedures used in clinical practice are unlikely to cause any major inconvenience to patients. In the Laccure pessary study,⁴⁴ there were no SAEs and vaginal itching was the most common AE.

There is a risk that patients will have no clinical benefit from the investigational device. This may cause patients to experience symptoms including vaginal itching, burning or soreness, pain during sexual intercourse, pain or discomfort when urinating, or abnormal vaginal discharge longer than necessary.^{1,45} However, fluconazole will be offered on Day 14 if any symptoms should still be present, thus avoiding any risk associated with long-term untreated VVC.

^a And on Day(s) 7, 9, 11, and 13 if receiving prolonged treatment

Protocol Version 3.0, 24Oct2018

LINK Medical Research | Protocol template

Version 2.0 | Effective date 17Apr2018

Subjects included in the study must refrain from using other intravaginal products, thus mitigating the risk of interactions with concomitant vaginally-administered products. The investigational device acts locally on the vaginal mucosa and most likely will most likely not affect any concomitant systemic treatment.

Taken together, as the anticipated levels of discomfort are transient and mild, and that risks associated with VVC are avoidable, the use of the investigational product appears to offer clinical benefits at a reasonable risk level.

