5.2.1 Rescue Medication

Fluconazole will be used as rescue medication in this investigation, and patients will receive a prescription for fluconazole if considered necessary to relieve their VVC symptoms on Day 14. Patients withdrawing at any point in the investigation may receive fluconazole if considered necessary by the Investigator. The dose of fluconazole will be decided by the Investigator on an individual basis. The use of rescue medication will be recorded in the eCRF.

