### **8.10 Proportion of patients receiving rescue treatment on Day 14**

The proportion of patients receiving rescue treatment (fluconazole, as defined in the CIP) on Day 14 is based on a binary variable which indicate whether a patient has used rescue treatment or not, i.e. as shown by collected CRF concomitant medication data, where start date of the rescue medication should be from or after Day 14. Start and stop date of use of such rescue medication will be presented in data listings.

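### SAP 8.8 ties recurrence to cure on Day 7 only, which contradicts the Day 14 definition of the recurrence endpoint for prolonged-treatment patients (xiii)

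*SAP*

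**What the plan says.** **Recurrence.** SAP 7.9.2 has two recurrence endpoints. Endpoint vii covers patients without prolonged treatment: cured on Day 7, then asked on Days 14 and 35. Endpoint xiii covers patients with prolonged treatment and is "defined as the proportion of patients clinically cured on Day 14 and thereafter responding" yes, asked on Days 21 and 42. SAP 3.2.1 and 6.1 give the same two definitions. SAP 8.8, under derived variables, has a single rule for both: "a recurred patient is defined as a patient clinically cured on Day 7 and thereafter responding" yes at the follow-up visits. It has no Day 14 version and states no denominator. The general rule in SAP 7.1.1 is that, unless stated otherwise, "the denominator for percentage calculations will be the total number of patients in the applicable analysis set, including patients with missing data".

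**Who is prolonged.** SAP section 4 and Protocol 3.1 agree: "Prolonged treatment at Day(s) 7, 9, 11, and 13 will be given to patients not cured at Day 7". Protocol 3.5.5 words the trigger differently, as VVC symptoms still being present at the Day 7 visit. Cure is a CVVS score of 3 or less, so a cured woman may still have a mild symptom.

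**Rescue.** Endpoint xiv is the proportion of prolonged patients prescribed fluconazole on Day 14. SAP 8.10 derives it from recorded use of rescue medication, where the "start date of the rescue medication should be from or after Day 14". Protocol 5.2.1 also allows rescue outside the Day 14 visit: "Patients withdrawing at any point in the investigation may receive fluconazole if considered necessary by the Investigator".

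**The concern.** Two definitions of the same endpoint stand in a final SAP, and they select different women. Section 8 is where a programmer looks for the rule to code. If 8.8 is coded, the recurrence rate after prolonged treatment could come out as zero whatever the women answered, and a zero recurrence rate flatters the product. SAP 7.2.2 calls the recurrence analyses important and adds a second per-protocol set for them, so the same derivation would feed that set too.

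SAP 7.11 lists the changes from the protocol, including the correction of a misplaced prolonged-treatment endpoint, but no change to recurrence. The Day 7 wording therefore looks like an omission and not a decision.

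For endpoint xiv, the question is whether the figure reported as Day 14 rescue would also contain rescue given later, for example at a withdrawal on Day 30.

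**Working it through.** The plan gives no figure to reproduce here. The check compares the rules, then sizes the effect.

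**1. The two rules for prolonged patients who later answer yes**

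| Day 7 | Day 14 | Counted by SAP 8.8 | Counted by xiii |
|---|---|---|---|
| not cured | cured | no | yes |
| not cured | not cured | no | no |
| cured, residual symptom | cured | yes | yes |
| cured, residual symptom | not cured | yes | no |

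Under SAP section 4 only the first two rows can occur. Rule 8.8 then counts nobody, so the numerator of xiii is 0. The last two rows can occur only under the symptom wording in Protocol 3.5.5. In that case the numerator is not forced to 0, but 8.8 still misses the first row and wrongly counts the fourth. For endpoint vii, 8.8 is correct.

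**2. How many women are involved**

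Inputs: 24 patients and a 70% Day 7 cure rate (SAP 5.1). Prolonged treatment is equated with no cure on Day 7. The documents give no Day 14 cure rate, so 40% to 70% is assumed.

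- Prolonged patients follow Binomial(24, 0.30): mean 24 × 0.30 = 7.2, 95% range 3 to 12.
- Cured on Day 14 at 40%: Binomial(24, 0.30 × 0.40 = 0.12), mean 2.9, 95% range 0 to 6.
- Cured on Day 14 at 70%: Binomial(24, 0.30 × 0.70 = 0.21), mean 5.0, 95% range 1 to 9.

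Between 0 and 9 women would be at risk in xiii, with about 3 to 5 expected.

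**3. Effect on xiii**

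For illustration, take 4 women cured on Day 14 and not on Day 7, of whom 2 answer yes. Exact (Clopper-Pearson) two-sided 95% intervals:

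- By the 7.9.2 definition: 2/4 = 50%, interval 6.8% to 93.2%.
- By 8.8 taken literally: 0/4 = 0%, interval 0 to 60.2%.

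**4. Effect of the unstated denominator**

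With women cured on Day 14 as the denominator, at 3 to 5 women one recurrence moves xiii by 1/5 = 20 to 1/3 = 33 points. If the SAP 7.1.1 default were applied, the denominator would be all 3 to 12 prolonged patients, and one recurrence would move it by 1/12 = 8 to 1/3 = 33 points. In the 4-woman example with 7 prolonged patients, the same 2 recurrences would read as 2/4 = 50% or 2/7 = 29%.

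**5. Endpoint xiv**

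The endpoint is a prescription at one visit, while 8.10 counts use with a start date on or after Day 14 and no end date. Follow-up ends at Day 42 (± 2 days), so the extra cases are rescue first used between the Day 14 visit and about Day 44. With 3 to 12 prolonged patients, one such case raises xiv by 8 to 33 points. In the other direction, a Day 14 prescription that was never taken would not be counted.

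**The case against.** The strongest reply is that 8.8 is a drafting slip that would do no harm. The Day 14 definition of xiii stands in three other SAP sections, one of them the analysis section itself. SAP 7.9.2 says that the analyses run on separate patient categories, and 8.8 points to follow-up visits that are specified elsewhere. A careful programmer would probably follow 7.9.2. This stands as far as likelihood goes: a reader might infer that xiii will be reported as 0%, and the documents do not support that. It does not remove the contradiction, because the dedicated derivation is the one that is wrong.

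On 8.10, a Day 14 prescription may reasonably be started a day or more later, so some allowance after Day 14 is needed. Counting later rescue raises the rescue rate, which works against the product, and start and stop dates are listed. All of this stands, and it makes the mismatch minor.

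A reader might also infer that xiii is flawed because women cured on Day 14 could receive fluconazole and then be counted as free of recurrence. Protocol 3.2.1 says that "fluconazole will be offered on Day 14 if any symptoms should still be present", and Protocol 5.2.1 says that "patients will receive a prescription for fluconazole if considered necessary to relieve their VVC symptoms on Day 14". But the study flow charts in both documents reserve fluconazole for women not cured on Day 14, and such cases may number zero. Keeping these women in the full analysis set regardless of rescue is a legitimate choice. The documents do not make this an error, and a split by fluconazole use is optional.

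**Conclusion.** SAP 8.8 is wrong as written for endpoint xiii. Followed literally, it gives a numerator of 0 if prolonged treatment goes only to women not cured on Day 7, and it uses the wrong visit if some are prolonged for residual symptoms with a CVVS score of 3 or less. The forced zero thus rests on SAP section 4 and Protocol 3.1; the wrong anchor does not.

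The SAP 8.10 mismatch with endpoint xiv is real but minor, and it does not favour the product where later use is added.

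The reach is limited. Endpoints xiii and xiv are secondary, SAP 7.9.2 plans no hypothesis test for binary secondary endpoints, and few women are involved. The counts rest on the 70% planning assumption and on an assumed Day 14 cure rate of 40% to 70%. The primary endpoint, Day 7 cure, is unaffected.

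**What to change.** Change the SAP only. The protocol planned last patient out in February 2019 and the SAP was final in January 2020, so rewording the protocol would probably serve no purpose.

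- **SAP 8.8.** Define recurrence separately. For vii: cured on Day 7, then yes on Day 14 or Day 35, reported for each day. For xiii: cured on Day 14, then yes on Day 21 or Day 42, reported for each day. In both, the denominator is the patients cured at the anchor visit, with missing answers shown.
- **SAP 8.10.** For xiv, count rescue prescribed at the Day 14 (+2 days) visit and report later use on a separate line. Use the prescription date if the eCRF holds one. Otherwise show the start date against the visit date, since a Day 14 prescription may be started later.
- **Optional.** A supportive count of Day 21 and Day 42 recurrence by fluconazole use among women cured on Day 14. The groups would be very small and selected on residual symptoms, so the count could not show what fluconazole did.

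The cost is a few lines of SAP text and at most one or two small tables. Apart from a possible prescription date, they use data the plan already collects.
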